#### **4.2 Handling of withdrawals (drop-outs) and missing values**

Discontinued or withdrawn subjects will not be replaced if they withdrew due an adverse event. Subjects withdrawn early from the study due to other reasons may be replaced (if there is sufficient time to complete the treatment period prior to the onset of the GPS). Data collected for subjects whose participation is terminated is evaluated with all data as collected until withdrawal and during a possible follow-up for safety.

Missing data for the primary variable on a by-subject level will be handled using multiple imputation methods

#### **4.3 Visit definition for analysis**

All scheduled visits will be analysed as defined in the protocol and the numbering is taken from the eCRF.

#### **4.4 Baseline**

A baseline measurement will be defined as the latest measurement obtained prior to the first administered dose of study medication.

#### **4.5 Reference day for the statistical analysis**

Day 1 is defined as the date of first administration of study medication. Study days for statistical analysis will be calculated relative to Day 1. There is no study Day 0 (day before first administration of study medication is day -1).

## 5 STATISTICAL ANALYSIS SPECIFICATION

### 5.1 Specifications related to whole analysis

#### 5.1.1 Tables

Data will be summarised using suitable descriptive statistics depending on the structure of the data.

Summary tables will be grouped by treatment group and by visit, and separated by relevant periods (e.g. treatment period, entire (truncated) GPS, peak GPS) if appropriate and reasonable.

If not specified otherwise, the following treatment groups will be included:

- PQ Grass (conventional posology),
- PQ Grass (extended posology),
- PQ Grass (pooled),
- Placebo (containing MCT),
- Placebo (without MCT), and
- Placebo (pooled).

To increase the readability of the summary tables and to separate the different periods, separate summary tables will be generated for different periods (e.g. treatment period, entire (truncated) GPS, peak GPS, etc.). Summary tables for all periods combined will be presented additionally whenever appropriate.

For quantitative variables, summary statistics will be created that include the number of subjects with data available, arithmetic mean, standard deviation (SD), median, first and third quartile, minimum, maximum.

For qualitative variables, the summaries will include the number and percentage of subjects for each outcome category.

If the analysis sets FAS and SAF are identical (i.e., planned and actual treatment assignments do not differ), all baseline summary tables will be displayed for the FAS only.

#### 5.1.2 Data listings

Individual data will be listed. In general, listings will be sorted by subject number. Each listing will contain the subject number, randomized treatment group, and most restrictive analysis set (PPS is more restrictive than FAS or SAF). The study period will be additionally displayed whenever applicable and reasonable.

Subject data listings for event-based data (e.g., adverse events or concomitant medications) will be sorted by subject number, by event start date and then alphabetically by reported term and coded term.

For all assessment dates, the study day relative to the first injection will be presented. For assessments analysed within the entire (truncated) or peak GPS (e.g., for start and end dates of adverse events within peak GPS), the day relative to the start of the entire (truncated) GPS and to the start of the peak GPS may be additionally displayed whenever reasonable.

### 5.1.3 Figures

If not specified otherwise, in all figures, the four treatment groups will be displayed separately, i.e. no pooled Placebo and no pooled PQ Grass group will be displayed.

## 5.2 Disposition of subjects

A summary table will be created including

- the number of screenings (including re-screenings),
- the number of subjects who were screened (i.e. signed the informed consent),
- the number of screen failures,
- the number of subjects who were randomised,
- the number and percentage of subjects who were treated,
- the number and percentage of subjects who completed the study including safety follow-up (only after 3 and 6 months follow-up data is available),
- the number and percentage of subjects who prematurely discontinued treatment, and
- the number and percentage of subjects who prematurely discontinued the study.

These categories will be displayed by randomised treatment group and overall and percentages will be calculated based on all randomised subjects, if applicable.

## 5.3 Demographics and baseline characteristics

Demographic information collected at Screening (Visit 1) will include age, sex, race, ethnicity, childbearing potential and methods of contraception, as well as smoking and alcohol consumption habits.

Height at Screening will be displayed in cm and weight at Screening in Kilograms (kg). Body Mass Index (BMI) will be calculated as

and displayed in  $\text{kg/m}^2$ .

Demographic data will be summarized by treatment group and overall for all analysis sets, and listed by subject. Childbearing potential and methods of contraception will only be tabulated for female subjects in the FAS.

## 5.4 Medical History and Concurrent Diseases

### 5.4.1 Definitions and conventions

A medical and allergy history including details regarding all illnesses, surgeries and any kind of allergies (to assess eligibility) at screening must be recorded in the eCRF. A full history for the 5 years prior to screening and any other significant medical history is to be documented. Concurrent diseases and medical history will be coded using the MedDRA dictionary (Medical Dictionary for Regulatory Activities) according to the version and update strategy as defined in the coding guideline for this study.

A concurrent disease is defined as any disease, for that either no stop date was documented or the stop date is later than the date of Visit 1. All other diseases are defined as medical history. Incomplete stop dates will be estimated using the first possible date in order to define

whether a disease is concurrent, i.e. it will be assumed that a disease is not ongoing at study start.

#### **5.4.2 Medical History and Concurrent Diseases (non-allergy related)**

Concurrent diseases and medical history not related to any allergy will be summarized by treatment group. In this summary table, the diagnoses and indications will be decoded by MedDRA preferred term (PT) and grouped under the respective system organ class (SOC). The SOCs and the PTs within will be sorted by decreasing frequency in the total column.

Separate tables will be created for non-allergy related medical history and concurrent diseases for the FAS.

Non-allergy related concurrent diseases and medical history will be listed by subject.

#### **5.4.3 Grass pollen allergy history and status at start of study**

Expressions of allergy will generally be summarized separately by whether the expression was ongoing at study start (expression of allergy occurred during the last grass pollen season before screening) or not.

Number and percentage of subject with the pre-printed expressions of grass pollen allergy (i.e. allergic conjunctivitis, allergic rhinitis, allergic cough, allergic asthma, allergic urticaria) will be provided by treatment group, differentiating further by severity, whether allergic treatment was required (i.e., anti-allergic treatment for symptom control was required for at least two consecutive seasons prior to the study) and / or allergic treatment was taken (i.e., repeated use of treatment for symptom control for at least two consecutive seasons prior to the study).

All grass pollen allergy history related information including start and end dates of expressions of grass pollen allergy will be listed by subject.

Grass pollen related concurrent diseases and medical history will be summarized for the FAS.

#### **5.4.4 Other allergy history**

Concurrent other allergies (ongoing at study start) will be summarized by treatment group and reported term (including "Other" as collected in the eCRF), differentiating further by severity and whether allergic treatment was required and/or taken for the FAS.

All other allergy history (past or present) will be listed by subject.

### **5.5 Previous and concomitant medication**

All prescription and over-the-counter medications taken by the subject during the study until study termination are recorded at each visit (scheduled or unscheduled) in the eCRF. Relief medications taken during the GPS will be recorded by the subject in the eDiary only and are not to be recorded as concomitant medication in the eCRF.

All previous and concomitant medications will be coded using the World Health Organization (WHO) Drug dictionary according to the version and the update strategy as defined in the coding guideline for this study.

Four relevant periods will be defined for previous and concomitant medications:

- Previous medications,
- concomitant medications during the whole study,

- concomitant medications during the treatment period, and,
- concomitant medications during the entire (truncated) GPS.

## 5.6 Other baseline characteristics

Other baseline measures are the results of Skin Prick Test (SPT), the results of spirometry, peak expiratory flow rate (PEFR), and grass-specific IgE for eligibility (ImmunoCAP). These data will be summarised by treatment group and overall for each analysis set, and listed by subject.

### 5.6.1 Skin Prick Test

A skin prick test (SPT) using various allergens will be performed at screening to assess eligibility of subjects. A standard negative control will be used and histamine control solution (1.0%) will be used for the positive control.

The reaction grade (negative, positive) will be displayed in a frequency table further differentiated by case history of symptoms during the 3 years prior to Visit 1.

### 5.6.2 Spirometry

Spirometry will be performed at screening to determine eligibility.

Summary statistics will be created for spirometry measurements at screening by treatment group. All spirometry results will be listed by subject.

### 5.6.3 Peak expiratory flow rate (PEFR)

Summary statistics will be created for the baseline PEFR only containing all subjects for the calculated peak exploratory flow ratio (best result divided by predicted result) in %.

All PEFR measurements will be listed by subject, visit and timepoint. Only the system calculated values will be listed.

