To explore the treatment effect of PQ Grass on the CSMS and TCS over the GPS.	CSMS averaged over the entire (or truncated) GPS. TCS averaged over the peak GPS. TCS averaged over the entire (or truncated) GPS.
To explore the treatment effect of PQ Grass on the dSS and dMS components of the CSMS over the GPS.	dSS component of the CSMS averaged over the peak GPS and entire (or truncated) GPS. dMS component of the CSMS averaged over the peak GPS and entire (or truncated) GPS.
To explore the treatment effect of PQ Grass on the dSS and dMS components of the TCS over the GPS.	dSS component of the TCS averaged over the peak GPS and entire (or truncated) GPS. dMS component of the TCS averaged over the peak GPS and entire (or truncated) GPS.
To explore the relationship between TSS during CPT and CSMS, TCS, dSS (for CSMS and TCS) and dMS (for CSMS and TCS) over the GPS compared to baseline.	TSS during CPT, CSMS, TCS, dSS (for CSMS and TCS) and dMS (for CSMS and TCS) over the peak and entire (or truncated) GPS for subjects with a positive CPT at baseline.
To evaluate well days and severe days during the GPS.	The probability of well days and severe days during the peak and entire (or truncated) GPS.
To evaluate TSS during CPT at the same dose eliciting a positive response at baseline.	Pre-GPS (Visit 12) TSS measured during CPT.
To evaluate immunological parameters.	Serum Ig responses (total IgE; grass-specific IgE and IgG4; specific IgE/total IgE and specific IgE/specific IgG4) at Visit 12 and Visit 15.
To evaluate the quality of life.	Rhinoconjunctivitis quality of life questionnaire with standardised activities (RQLQ(S)) measured within the GPS.

Objectives	Endpoints
Safety	
To evaluate the safety and tolerability of PQ Grass in subjects with grass pollen induced seasonal allergic rhinitis and/or rhinoconjunctivitis.	
Frequency, severity and relationship of AEs to treatment.
 
Frequency of AEs leading to premature discontinuation from treatment or study.
 
Frequency of AESI.
 
Changes in clinical laboratory values (chemistry, haematology, urinalysis) between screening and Visit 15.
 
Changes in vital signs (all subjects) and PEFr (only in subjects with past or current asthma) at all treatment visits.

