This is an exploratory field study which will aim to randomise 150 subjects, with approximately 50, 50, 25 and 25 subjects randomised to PQ Grass 27600 SU (conventional posology), PQ Grass 27600 SU (extended posology), placebo containing MCT and placebo without MCT, respectively. This number is considered adequate for an exploratory study to verify the assumptions for the coefficient of variation (CV) of the placebo and the average reduction in CSMS after treatment with PQ Grass compared to placebo (both expressed as percentages and as absolute differences) during the peak GPS. The findings from this exploratory study will support the sample size calculations of a subsequent pivotal Phase III study for PQ Grass (PQGrass306).

The primary endpoint of the study will be the CSMS averaged over the peak GPS.

The difference in CSMS between PQ Grass (conventional posology) and placebo (i.e., the placebo containing MCT group and the placebo without MCT group) and the difference between PQ Grass (extended posology) and the placebo groups will be evaluated using parametric (i.e., linear mixed effects model) / non-parametric models as appropriate. The 2 placebo groups will both be combined and analysed as separate groups if there is <5% effect-size difference and similar variability between the 2 groups. Otherwise, they will only be analysed as independent groups.

Secondary efficacy endpoints derived from the CSMS, TCS, daily symptom score (dSS) and daily medication score (dMS) (for both the CSMS and TCS) and for the peak/entire (or truncated) GPS, immunological responses, probability of well days and quality of life will be evaluated using comparable linear mixed effects model and sensitivity analyses as in the primary efficacy analysis.

The frequency, relationship and severity of AEs and frequency of premature discontinuations from treatment or study due to AEs will be assessed within each treatment group. Changes in vital signs, clinical laboratory parameters and peak expiratory flow rate (PEFR) in subjects with past or current asthma will be analysed using descriptive statistics and 2-sided 95% confidence intervals (CIs) within each treatment group. All other safety data will be analysed descriptively.

Trial Oversight Committee: Yes.

Adjudication Committee: Yes.

Schedule of activities

	Period 1 Screening	Period 2 Randomisation and Treatment					Period 3 Pre/during/end of GPS Assessments				Period 4	

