## 5.8 Safety

Analysis of all safety and tolerability variables will be based on the safety population (i.e., all subjects who received at least 1 dose of IMP). Summary statistics will be provided for safety variables. Alert ranges will be defined for laboratory values lying outside the normal range to a clinically relevant degree. Any measurement fulfilling these criteria will be presented in subject listings.

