#### 5.8.4 Vital signs

Vital signs (systolic and diastolic blood pressure, pulse rate, respiratory rate, and body temperature) will be measured after the subject has been in the supine position for at least 5 minutes at Visit 1 to Visit 15.

Summary statistics will be created per vital sign parameter and visit/timepoint (pre- and post-injection) for all scheduled treatment visits by treatment group including the absolute values per visit/timepoint and the absolute change from baseline.

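### The SAP specifies no group summary of PEFR change at the treatment visits in subjects with past or current asthma, and no 95% CI, although the protocol makes this change a safety endpoint

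*SAP*

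**What the plan says.** **Protocol.** The safety rows of the objectives and endpoints table include "Changes in vital signs (all subjects) and PEFr (only in subjects with past or current asthma) at all treatment visits". The statistical methods section of the synopsis gives the analysis: "peak expiratory flow rate (PEFR) in subjects with past or current asthma will be analysed using descriptive statistics and 2-sided 95% confidence intervals (CIs". This is to be done separately for every arm, and the same sentence covers vital signs and clinical laboratory parameters. The schedule of activities marks PEFR at every site visit, Visits 1 to 15.

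**SAP.** PEFR is introduced in section 5.6 as a baseline characteristic: "Other baseline measures are the results of Skin Prick Test (SPT), the results of spirometry, peak expiratory flow rate (PEFR" and so on. Section 5.6.3 then says "Summary statistics will be created for the baseline PEFR only containing all subjects for the calculated peak exploratory flow ratio", defined as the best result over the predicted result in per cent. It continues: "All PEFR measurements will be listed by subject, visit and timepoint". Section 5.8 opens with a general line, "Summary statistics will be provided for safety variables", but none of its subsections names PEFR.

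**The concern.** The only PEFR summary that the SAP specifies differs from the protocol endpoint in three ways. It is at baseline rather than at the treatment visits. It is in all subjects rather than in those with past or current asthma. It describes a level rather than a change. The promised interval is missing as well.

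Subjects with well-controlled asthma may enter the trial and receive injected allergen, and the protocol singled out airflow change in subjects with past or current asthma. If the SAP is followed as written, the report will contain no group-level statement on that change. A shift in airflow too small to be recorded as an adverse event could then be found only by working through individual values.

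**Working it through.** No sample size, power or error-rate figure is involved, so there is nothing to recompute. The check sets the protocol's commitment against each place in the SAP that could meet it.

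| Element | Protocol synopsis | SAP |
|---|---|---|
| Role of PEFR | Safety endpoint | Baseline characteristic (5.6, 5.6.3) |
| Population | Past or current asthma | All subjects; no asthma subset defined for PEFR |
| Time | All treatment visits | Baseline for the summary; all visits for the listing only |
| Quantity | Change | Level, as % of predicted |
| Interval | Two-sided 95% CI within group | None |

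1. **Could another part of SAP 5.8 supply the summary?** Its subsections cover exposure and compliance, adverse events, safety laboratory, vital signs, physical examination and other safety data. The last of these (5.8.6) covers pregnancy tests only. The SAP's contents list shows no other PEFR section.
2. **Was post-baseline change left out for the whole endpoint line?** No. Vital signs share that line with PEFR, and SAP 5.8.4 handles them by visit: "Summary statistics will be created per vital sign parameter and visit/timepoint (pre- and post-injection"), with absolute change from baseline. PEFR has no counterpart to this text.
3. **Is a 95% CI given elsewhere?** The default statistics in SAP 5.1.1 are the number of subjects, mean, SD, median, quartiles, minimum and maximum, with no CI. The only confidence level that the SAP states is 80%, for efficacy (5.7.1.4) and immunology (5.7.2.6). Sections 5.8.3 and 5.8.4 give no CI, so the protocol's intervals for laboratory and vital sign changes are absent too.
4. **Extent.** Injections are given at Visits 2 to 11, which is 11 − 2 + 1 = 10 treatment visits, in all four arms.
5. **Precision.** The documents give neither the number of subjects with past or current asthma nor an SD of PEFR change. No CI width is calculated, because it would rest entirely on invented inputs.

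**The case against.** The best defence has four parts.

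- **The general safety sentence.** SAP 5.8 promises summary statistics for safety variables, and the protocol classes PEFR change as one. The baseline-only wording sits in a baseline section, so it might limit that section alone. This reading is possible but weak. Section 5.6.3 also sets out the listing for all visits, so it is not confined to baseline. The general sentence supplies no subset, no change and no interval, and a programmer would follow the specific rule.
- **The values are reported.** A reader might infer from the mismatch that the endpoint would go unreported or be lost altogether. The documents do not support that, since every PEFR measurement is to be listed by subject, visit and timepoint. What is missing is the group summary of change.
- **Clinical reactions are covered.** A reader might also infer that airway reactions would be hidden. That does not follow either. Systemic adverse events and adjudicated events of special interest are summarised (SAP 5.8.2.1 and 5.8.2.2), and adverse events are tabulated after each injection, including within 24 hours (5.8.2.3). This part of the defence stands. It confines the concern to airflow changes not recorded as adverse events.
- **Another plan may cover it.** SAP 2.1 mentions a separate plan for additional exploratory and sensitivity analyses. Nothing indicates that it covers this endpoint, and SAP section 2 describes the present document as giving all details of the final analysis.

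On the vital sign and laboratory intervals, it is fair to say that within-group CIs add little in an exploratory study whose SAP already plans summary tables for them.

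**Conclusion.** The SAP is wrong as written on this point. A specific rule in 5.6.3, with nothing in 5.8 to complement it, leaves a declared safety endpoint without the analysis that the protocol promises. The SAP neither acknowledges nor justifies a departure.

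The missing item is the summary of PEFR change over ten treatment visits in the asthma subset, by treatment group, with its 95% CIs. The individual data and the adverse event tables remain. The absent CIs for changes in vital signs and laboratory values are a minor, separate discrepancy and add no weight to the PEFR point.

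The conclusion rests on the text of the two documents and on the assumption that no unseen plan contains the analysis. It does not depend on how many subjects have asthma. That number decides how informative the summary would be, and a small subset would give wide intervals. The point should be corrected, but it does not touch the primary efficacy analysis.

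**What to change.** Add a PEFR subsection to SAP 5.8, restricted to Safety Set subjects with past or current asthma:

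- Define the subset from the recorded medical and allergy history.
- Tabulate PEFR as % of predicted, the scale already used in 5.6.3, and its change from the baseline defined in SAP 4.4, by treatment group and treatment visit.
- Give the usual descriptive statistics plus the mean change with its two-sided 95% CI. The protocol asks for no more than this; in particular, it does not promise an analysis of PEFR from before to after each injection.

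Add the 95% CI to the change tables for vital signs and laboratory values. Section 5.8.3 should also say that its tables include the change from screening to Visit 15, which it does not now state.

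If the sponsor intends to omit any of this, the SAP should state the departure from the protocol and give the reason. The cost is one more safety table and CI columns in existing ones. All the data are already collected, and the PEFR values are already to be listed.
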